1.2. Study Schema

A Phase 3, Multicenter, Open-Label Extension Study of the Long-Term Safety of ARQ-151 Cream 0.15% and ARQ-151 Cream 0.05% in Subjects with Atopic Dermatitis

Up to approximately 1500 subjects that have completed the 4-week treatment period in studies ARQ-151-311 or ARQ-151-312 or ARQ-151-315 and are willing and qualified to enroll in this long-term extension study will receive ARQ-151 cream 0.15% (ARQ-151-311/312 roll-overs) or ARQ-151 cream 0.05% (ARQ-151-315 roll-overs).

** Under Amendment 1, 24 Week Treatment Period for Cohort-Week 24, Clinic Visits, and Phone Contact Weeks 4, 12, 18, 24

1.3. Schedule of Visits and Assessments

Study Procedure	Day 1	Wk 4	Wk 12	Wk18	Wk 24 ^t	Wk 30	Wk 36	Wk 44	Wk 52/ET
Visit #	1(Week 4) of ARQ-151-311 or ARQ-151-312 or ARQ-151-315	2	3	Phone Visit	4	Phone Visit	5	Phone Visit	6
Visit Window		+/- 3 days	+/- 7 days	+/- 7 days	+/- 7 days	+/- 7 days	+/- 7 days	+/- 7 days	+/- 7 days
Informed consent/assent	X								
Physical examination ^a	X ^s	X			X				X
I/E criteria	X								
Hematology, Serum Chemistries, and Urine Analysis ^b	X ^s				X				X
Vital signs, height, weight ^c	X ^s	X	X		X		X		X
vIGA-AD, EASI, BSA, SCORAD ^d	X ^s	X	X		X		X		X
WI-NRS pruritus ^e	X ^s								
POEM ^f	X ^s	X	X		X		X		X
Local Tolerability Assessment ^g	X	X	X		X		X		X
CDI-2, PHQ-8, PHQ-A, C-SSRS ^h	X ^s	X	X		X		X		X
DLQI, CDLQI, IDQOL, DFI ⁱ	X ^s	X	X		X		X		X
Medical Photography ^j	X ^s	X	X		X		X		X
Urine pregnancy test ^k	X ^s	X	X		X		X		X
PK draws ^l									X

Study Procedure	Day 1	Wk 4	Wk 12	Wk18	Wk 24 ^t	Wk 30	Wk 36	Wk 44	Wk 52/ET
Visit #	1(Week 4) of ARQ-151-311 or ARQ-151-312 or ARQ-151-315	2	3	Phone Visit	4	Phone Visit	5	Phone Visit	6
Visit Window		+/- 3 days	+/- 7 days	+/- 7 days	+/- 7 days	+/- 7 days	+/- 7 days	+/- 7 days	+/- 7 days
Dispense study medication kit ^m	X	X	X		X		X		
Drug application and Parents/Caregivers training in clinic	X								
Dispense/review diary ⁿ	X	X	X		X		X		X
Maintenance Dosing Determination ^o		X	X		X		X		
Weigh study medication ^p	X	X	X		X		X		X
Compliance Determination ^q		X	X		X		X		X
Adverse event assessment ^r	X	X	X	X	X	X	X	X	X
Concomitant medications	X	X	X	X	X	X	X	X	X
Study Exit					X ^t				X

^a Limited physical examination: skin, lungs, and heart only

^b Hematology, Serum Chemistries, and Urine Analysis will only be done in subjects \geq 12 years of age at time of enrollment in the preceding study.

^c Height will be collected at Day 1 only for subjects \geq 18 years old and at every clinic visit for subjects $<$ 18 years old. Weight should be obtained using a calibrated weight scale and the same scale should be used for a subject throughout the duration of the study. The subject should remove shoes and heavy clothing (sweaters or jackets), and empty pockets. The subject should stand with both feet in the center of the scale with their arms at their side and hold still. Record the weight to the nearest decimal fraction (for example, 25.1 kilograms). For subjects $<$ 18 years of age, measure the weight in triplicate and report the average weight in EDC. A 5% or greater weight loss (whether or not intentional or otherwise explained) should be reported to the medical monitor.

^d The vIGA-AD assessment will be a 5-point scale ranging from clear (0) to severe (4) and is evaluated for the entire body except the scalp, palms, and soles. EASI takes into account overall severity of erythema, infiltration/papulation, excoriation, and lichenification, in addition to extent of BSA affected. The 4 clinical signs will be graded on a 4-point scale (0 [absent] to 3 [severe]) for 4 body regions (head and neck, upper extremities, lower extremities, and trunk). Total EASI score will be calculated as a sum of scores of all 4 body regions. EASI total score will range from 0 (absent) to 72 (severe). Total BSA affected by AD will be determined for all body surfaces except the scalp, palms and soles. vIGA-AD should be completed prior to other physician assessments. SCORAD total score will range between 0 and 103.

Footnotes from table above:

- ^c The WI-NRS pruritus questionnaire will be completed once a week at home utilizing a diary. **The WI-NRS will be self-reported by subjects for subjects ≥ 6 years of age, and reported by parent/guardian for subjects <6 years of age.** During the Phone Visits at Weeks 18, 30, and 44 a reminder will be given to subjects to complete the WI-NRS pruritus questionnaire once a week.
- ^f POEM will be completed by all subjects either by self or by proxy completion (for children unable to read and/or understand the POEM questionnaire, the parent/guardian/caregiver will complete the questionnaire).
- ^g At Day 1 only, local tolerability assessments should be recorded prior to study drug application for the Investigator assessment of skin irritation (Berger and Bowman skin irritation score) and 10-15 minutes post-drug application for the Subject's '0-3' burning/stinging assessment. **Note for investigator tolerability assessments: reactions at the site of product application should be differentiated from the preexisting inflammation associated with the subject's atopic dermatitis. For subject tolerability assessments after Day 1, the subject will assess burning/stinging (0-3 score) 10-15 minutes post drug application based on recall of the last drug application.** For subjects <6 years of age, parents will complete.
- ^h Adolescents and adults (12 years and older) will complete the C-SSRS (12 years old of age and older). Adults will complete the PHQ-8. Adolescents (ages 12 to 17 years of age, inclusive) will complete the PHQ-A (PHQ-9 modified for Adolescents). Parents/caregivers will complete the parent report (CDI-2) for children 6-11 years of age, inclusive. Subjects will continue with the assessments specific to their age group at the time of consent/assent at Screening of the preceding study.
- ⁱ The DLQI will be completed by subjects ≥ 17 years of age (based on age at start of preceding studies ARQ-151-311/312). The CDLQI will be completed for subjects ≥ 4 years of age and ≤ 16 years of age (based on age at start of preceding studies ARQ-151-311/312/315). The Infants' Dermatitis Quality of Life (IDQOL) will be completed by parents/caregivers for subjects < 4 years (based on age at start of parent preceding studies ARQ-151-315). The Dermatitis Family Impact Questionnaire (DFI) will be completed by parents/caregivers for all subjects ≥ 2 years of age and ≤ 17 years of age. Subjects will continue with the assessments specific to their age group at the time of consent/assent at Screening of the preceding study. DFI is not to be conducted for subjects who were ≤ 17 years of age in the ARQ-151-311/312 studies and turned 18 years of age prior to enrollment into ARQ-151-313.
- ^j Photography will be performed using Canfield equipment on all subjects at all study sites. All efforts will be made to de-identify the subjects. Subjects who are unwilling to participate in the medical photography will be allowed to opt out of this procedure and documented on the informed consent. See Photography Manual for details.
- ^k A urine pregnancy test will be administered to all females of child-bearing potential. A negative result is required for continued participation in the study, and results must be available prior to dispensing of study drug at each visit.
- ^l For all subjects ≥ 12 years old entering this study under Amendment 1 a single PK trough draw will be collected at Week 52/ET. Ensure study medication was not applied in the area where PK will be drawn.
- ^m It is expected that kits will be dispensed based on %BSA affected and subject's age. Subjects who turn 6 years old during the study will switch to ARQ-151 cream 0.15% at their first scheduled post-birthday visit. See IP Handling Manual for details. Under Amendment 1, this is the final visit for Cohort-Week 24 and no kits will be dispensed at this visit.
- ⁿ Dispensing of IP is allowed, if needed. Study site should review IP kit to ensure sufficient IP is available until the next visit and only dispense additional IP if needed. **All subjects will continue study medication application in the areas identified and treated as per the body diagram in the preceding study for the first 4 weeks of the current study (ARQ-151-313).**

Footnotes from table above:

^o Beginning at the Week 4 visit, any subject who achieves vIGA-AD of ‘0-clear’ as confirmed by the Investigator at a scheduled or unscheduled clinic visit, will switch to twice weekly (BIW) maintenance treatment. For maintenance therapy, study medication will be applied on two nonconsecutive days per week (e.g. Monday and Thursday) to areas commonly and/or most recently affected by AD, and any areas where AD is developing. Subjects receiving maintenance treatment who experience AD worsening (signs and symptoms) for 1 week despite dosing twice weekly will phone the clinical study site, resume daily dosing, and complete the subject diary accordingly. The phone call (but not a clinic visit) is required to resume daily dosing. At clinic visits, subjects receiving maintenance treatment may continue twice weekly maintenance dosing if vIGA-AD is either ‘0-clear’ or ‘1-almost clear’. Subjects will resume daily dosing if vIGA-AD ≥ 2 , and can resume daily dosing if signs/symptoms of AD are not adequately controlled with maintenance therapy despite vIGA-AD of ‘1-almost clear’. Under Amendment 1, maintenance dosing determination will not be conducted at Week 24 for Cohort-Week 24.

^p The entire kit (every tube) should be weighed and recorded at every visit. See IP Handling Manual for details.

^q Compliance calculation is described in the IP Handling Manual

^r Any emergent AEs will be followed in the clinic for up to one month at the Investigator’s discretion until resolved or otherwise judged as clinically stable.

^s This data will be obtained from Week 4 of ARQ-151-311/312/315 Study and used as the Day 1 data for this long-term safety study (ARQ-151-313).

^t Under Amendment 1, this is the final visit for Cohort-Week 24 from ARQ-151-311 and ARQ-151-312.

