2.4.2. Risks and/or Benefits to Subjects

A favorable local and systemic benefit-risk profile has been observed in prior studies of ARQ-151 cream. Subjects 2 years of age and older enrolled in this study, may see an improvement in their atopic dermatitis with ARQ-151 cream 0.15% or ARQ-151 cream 0.05%, based on the activity of doses tested in atopic dermatitis (0.05% and 0.15%) and psoriasis (0.15% - 0.5%), and approval of a less potent topical PDE-4 inhibitor (crisaborole) for atopic dermatitis. Subjects may also see some benefit of ARQ-151 cream based on a potentially moisturizing effect of the formulation.

Oral roflumilast has been used for almost a decade in the treatment of COPD exacerbations and its safety profile is well-documented. The known adverse effects of oral treatment in the COPD population (nausea, vomiting, diarrhea, weight loss, psychiatric AEs (see [Section 2.3.2](#)) can be readily monitored as specified in this protocol. The profile that is emerging from studies of topical roflumilast appears different from the safety and tolerability profile of oral roflumilast. While oral PDE-4 inhibitors (DALIRESP, OTEZLA) have been associated with, in particular, a moderate incidence of GI AEs, these AEs, and perhaps others, appear to be reported far less frequently with topical PDE-4 inhibitors, including EUCRISA®, and ARQ-151 cream to date in clinical trials. For ARQ-151 cream, this may be related to the lack of 'peak to trough' C_{max} variation, lower C_{max} values than observed following oral administration, or bypassing of the gastrointestinal tract with topical administration.

This study has been designed with adequate safety monitoring practices (i.e., physical examinations, vital signs/weight, local skin toleration assessments, hematology, serum chemistry, urinalysis, PHQ-A/PHQ-8, CDI-2, C-SSRS and AE reporting). In addition, parents/caregivers of subjects 2 to 5 years of age will be advised to promptly report any changes in behavior that could signal psychological distress or emotional distress.

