4. INVESTIGATIONAL PLAN

4.1. Overall Study Design and Plan

This is a Phase 3, open-label, single-arm, long-term safety study in which ARQ-151 cream 0.15% or ARQ-151 cream 0.05% is applied QD x 24 (Cohort-Week 24) or 52 weeks to subjects with mild to moderate atopic dermatitis (except for time on BIW maintenance therapy).

- Eligible subjects will enroll into the long-term safety study on the same day as the Week 4 visit of the preceding study (ARQ-151-311 or ARQ-151-312 or ARQ-151-315).
- Subjects/caregivers will apply ARQ-151 cream 0.15% for subjects \geq 6 years old or ARQ-151 cream 0.05% for subjects 2-5 years old.
- If a 5 year-old subject turns 6 years-old during this study, the subject will be switched from ARQ-151 cream 0.05% to ARQ-151 cream 0.15% at his/her first scheduled post-birthday visit. Dose reduction back to 0.05% is not permitted.
- The study drug will be applied QD for 24 (Cohort-Week 24) or 52 weeks to all AD affected areas and any newly appearing AD lesions that arise during the study, except on the scalp (unless entering BIW maintenance therapy, as described below).
- **For the first 4 weeks of study ARQ-151-313, all subjects will apply study medication QD in the areas identified and treated as per the body diagram in the preceding study (ARQ-151-311/312/315).** Beginning at the Week 4 visit, any subject who achieves vIGA-AD of '0-clear' as confirmed by the Investigator at a scheduled or unscheduled clinic visit, will switch to twice weekly (BIW) maintenance treatment. For maintenance therapy, study medication will be applied on two nonconsecutive days per week (e.g. Monday and Thursday) to areas commonly and/or most recently affected by AD, and any areas where AD is developing. Subjects receiving maintenance treatment who experience AD worsening (signs and symptoms) for 1 week despite dosing twice weekly will phone the clinical study site, resume daily dosing, and complete the subject diary accordingly. The phone call (but not a clinic visit) is required to resume daily dosing. At clinic visits, subjects receiving maintenance treatment may continue twice weekly maintenance dosing if vIGA-AD is either '0-clear' or '1-almost clear'. Subjects will resume daily dosing if vIGA-AD \geq 2, and can resume daily dosing if signs/symptoms of AD are not adequately controlled with maintenance therapy despite vIGA-AD of '1-almost clear'.

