5.1. Safety Assessments

This study assesses the long-term safety and efficacy of ARQ-151 cream. Safety will be determined by evaluating physical examinations, local tolerability assessments, vital signs/weight, clinical laboratory parameters (subjects ≥ 12 years old), either PHQ-8 (adults, ≥ 18 years old) or modified PHQ-A (adolescents, 12-17 years old) or Children's Depression Inventory 2 (CDI-2, parent report for children 6-11 years old, inclusive), C-SSRS (12 years and older) and AEs as outlined in the Schedule of Visits and Assessments ([Section 1.3](#)).

Additional evaluations/testing may be deemed necessary by the PI and/or the Sponsor for reasons related to subject safety.

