5.1.1. Day 1 Visit

[figure not shown]
At Day 1 (Week 4 of the ARQ-151-311 or ARQ-151-312 or ARQ-151-315 study) subjects from these preceding studies will be provided details of study requirements and sign an informed consent. Subjects will continue with the safety and efficacy assessments specific to their age group at the time of consent/assent at Screening of the preceding study. Medical and surgical history collected in the preceding study will be used in the ARQ-151-313 study. Only new information and updates will need to be collected at Day 1 visit. Atopic dermatitis assessments (vIGA-AD, BSA, EASI, SCORAD), physical examination, vital sign measurements (blood pressure, heart rate, and temperature), WI-NRS, CDI-2, DLQI, CDLQI, IDQOL, DFI, C-SSRS, POEM, and PHQ (-8 or -A), medical photography, laboratory tests: hematology, chemistry, urinalysis and a pregnancy test for female subjects of child bearing potential will be obtained at Week 4 visit of ARQ-151-311 or ARQ-151-312 or ARQ-151-315 study and will serve as the Day 1 for ARQ-151-313 subjects. The baseline value for safety and efficacy will be the last observation prior to the first dose of ARQ-151 cream in either the ARQ-151 preceding study (ARQ-151-311 or ARQ-151-312 or ARQ-151-315), or this study.

All subjects will retain their Subject ID from the preceding study which will be entered into the electronic subject tracking system for this long-term safety study.

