5.1.9. Children's Depression Inventory 2 (CDI-2)

The CDI-2 Assessment will be performed according to the Schedule of Visits and Assessments ([Section 1.3](#)) for subjects 6 to 11 years old, inclusive.

The CDI-2 quantifies depressive symptomatology using reports from children/adolescents, teachers, and parents or caregivers. It is recommended for use in initial evaluation and is appropriate when there is a need for an assessment and robust description of a child's depressive symptoms.

This study will use the CDI Parent Report Form. An example of the Parent report form is presented in [Appendix 3](#).

A subject with a CDI-2 raw score of ≥ 21 for females and ≥ 22 for males should be referred to a mental health professional for evaluation.

A subject with a CDI-2 raw total score of ≥ 32 should be referred to a mental health professional, and the Investigator in consultation with the mental health professional should consider interruption or discontinuation of the study drug.

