5.1.10. Columbia-Suicide Severity Rating Scale (C-SSRS)

C-SSRS Assessments will be performed according to the Schedule of Visits and Assessments ([Section 1.3](#)) for subjects 12-years old and older.

The administration schedule of the C-SSRS will be:

- The “Since Last Visit” version ([Appendix 4](#)) will be used at all visits.
- A score greater than 0 at the Baseline visit in suicidal ideation may indicate the need for mental health intervention. The investigator should not enroll the subject in the study.
- Any score greater than 0 in the suicidal ideation score may indicate the need for mental health intervention. The Investigator should give consideration for the subject to discontinue from the study drug and prompt referral to an identified mental health professional and/or an appropriate emergency room. The Medical Monitor should be contacted.

The C-SSRS administer will be trained via the C-SSRS training video. A training certificate for the administer(s) will be on file in the trial master file at the study site.

The Investigator must review the completed C-SSRS. A qualified mental health care provider must be available, immediately if needed, to refer the subject for further evaluation.

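### Psychiatric scales follow age at parent-study Screening while dose follows attained age, so a child who turns 6 moves to 0.15% with no scheduled psychiatric scale

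*Protocol*

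**What the plan says.** **Scales.** The Protocol 1.3 schedule places the CDI-2, PHQ-8, PHQ-A and C-SSRS in one row, given at every clinic visit. Footnote h assigns the CDI-2 parent report to ages 6-11, the PHQ-A to 12-17, the PHQ-8 to adults and the C-SSRS to 12 and older. Ages 2-5 have no scale. The footnote then fixes the age group: "Subjects will continue with the assessments specific to their age group at the time of consent/assent at Screening of the preceding study". Protocol 5.1.1 repeats the rule: "Subjects will continue with the safety and efficacy assessments specific to their age group at the time of consent/assent at Screening" of the preceding study. SAP 5.5 sets the CDI-2, PHQ-A and PHQ-8 by age at the start of the preceding study.

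**Dose.** Protocol 4.1 goes by attained age. When a 5-year-old turns 6, "the subject will be switched from ARQ-151 cream 0.05% to ARQ-151 cream 0.15% at his/her first scheduled post-birthday visit", and the child may not go back to the lower strength.

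**What the CDI-2 triggers.** Protocol 5.1.9 sets referral at a raw score of 21 or more (girls) or 22 or more (boys). At 32 or more, "the Investigator in consultation with the mental health professional should consider interruption or discontinuation of the study drug". Protocol 4.7.5 and 5.9 carry the same upper threshold.

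**Risk statement.** Protocol 2.4.2 says the known adverse effects of oral roflumilast, psychiatric events among them, "can be readily monitored as specified in this protocol", and names the CDI-2 and C-SSRS among the safety measures. For ages 2 to 5 it adds that caregivers "will be advised to promptly report any changes in behavior that could signal psychological distress or emotional distress".

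**The concern.** Scale and dose run on different clocks. At the sixth birthday the child receives the cream strength used in 6-year-olds but not the depression screen that the protocol attaches to 6-year-olds on that strength. Without a score, the CDI-2 referral and consider-stopping thresholds cannot be reached. For these children the protocol's statement that psychiatric effects can be monitored as specified has no scheduled scale behind it.

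What is at stake is individual screening. The primary endpoints are AEs and serious AEs, and SAP Section 2 lists the psychiatric scales under other safety endpoints.

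A second, smaller point has the same source. A subject screened at 11 who turns 12 keeps the CDI-2 parent report and is probably not scheduled for the C-SSRS.

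**Working it through.** The plan gives no figure to reproduce. The check applies the rules to two children and then sizes the gap per child.

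**Rule check**

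| Screening age | Attained age | Cream | Scheduled psychiatric scale |
|---|---|---|---|
| 6 (311/312) | 6 | 0.15% | CDI-2 at every clinic visit |
| 5 (315) | 6, after switch | 0.15% | none |
| 11 | 12 | 0.15% | CDI-2; C-SSRS probably not |

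The last row says probably because Protocol 5.1, 5.1.10 and SAP 13.7 give the C-SSRS for 12 and older with no age anchor, and SAP 5.5 has no C-SSRS entry. Protocol 5.1.10 does defer to the schedule ("C-SSRS Assessments will be performed according to the Schedule of Visits and Assessments"), where footnote h fixes the group. The 17 CDI-2 items in Protocol Appendix 3 include none on suicidality.

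**Size at age 6**

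Inputs from the Protocol 1.3 schedule: clinic visits at Weeks 4, 12, 24, 36 and 52; last dispensing at Week 36. Assumptions: birthdays evenly spread over 52 weeks from Day 1 of this study, visits on target day, the switch made at a clinic visit, no dropout.

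| Birthday in weeks | Width | Switch at | Weeks on 0.15% | Clinic visits after switch visit | Of these, before Week 52 |
|---|---|---|---|---|---|
| 0-4 | 4 | 4 | 48 | 4 | 3 |
| 4-12 | 8 | 12 | 40 | 3 | 2 |
| 12-24 | 12 | 24 | 28 | 2 | 1 |
| 24-36 | 12 | 36 | 16 | 1 | 0 |

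- Share switching: 36/52 = 69.2%. If 10% to 30% left before the switch (an assumption), 69.2% × 0.9 = 62% and 69.2% × 0.7 = 48%.
- Mean weeks on 0.15%: (4×48 + 8×40 + 12×28 + 12×16)/36 = 1040/36 = 28.9.
- Mean visits after the switch visit: (4×4 + 8×3 + 12×2 + 12×1)/36 = 76/36 = 2.1.
- Of these, before study exit: (4×3 + 8×2 + 12×1 + 12×0)/36 = 40/36 = 1.1. One third of switchers (12/36) have none.
- CDI-2 forms under the fix, counting the switch visit: (4×5 + 8×4 + 12×3 + 12×2)/52 = 112/52, or about 215 per 100 children aged 5 at Day 1.

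Counting from age 5 at parent-study start adds children who turn 6 during that 4-week study, taken to start 0.15% at Day 1. The share becomes 40/52 = 77%, with means of (4×52 + 1040)/40 = 31.2 weeks and (4×5 + 76)/40 = 2.4 later visits.

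**Size at age 12**

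Of subjects aged 11 at Day 1, 24/52 = 46% in Cohort-Week 24 turn 12 by Week 24; essentially all in the 52-week cohort do by Week 52. Starting the C-SSRS at the next clinic visit adds (4×3 + 8×2 + 12×1)/52 = 40/52, or 77 forms per 100 in Cohort-Week 24. Of these, (4×2 + 8×1)/52 = 16/52, or 31 per 100, come before exit. In the 52-week cohort the total is (4×5 + 8×4 + 12×3 + 12×2 + 16×1)/52 = 128/52, or 246 per 100.

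**The case against.** **The freeze is deliberate and uniform.** It also covers laboratory tests, quality-of-life scales and the EASI formula, and it protects change scores. That stands as a general reason. It has little force here, because these children have no earlier series on the scale to be added. The rule is not absolute either: the DFI is dropped for subjects who turn 18 before enrolment.

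**Much cover remains.** This stands, and it rules out inferring that switchers go unmonitored. AEs are collected at clinic and phone visits, with an open question at clinic visits (Protocol 5.7.4). Staff review the caregiver diary. A child aged 5 at parent-study start completes the CDLQI, which has mood and sleep items, though tied to the skin. Protocol 5.9 has a suicidality referral for all ages, and Protocol 5.1 allows discretionary testing: "Additional evaluations/testing may be deemed necessary by the PI and/or the Sponsor for reasons related to subject safety". The caregiver advice and behaviour rule for ages 2 to 5 may also continue, since the freeze in Protocol 5.1.1 could be read to carry them past the birthday. The text does not say.

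**The risk is indirect.** The psychiatric signal comes from oral roflumilast, and Protocol 2.4.2 says the topical profile appears different. A reader might infer that systemic exposure triples with the strength. No exposure figures visible in the documents support that, and clear subjects move to twice-weekly dosing. Even so, the sponsor chose the CDI-2 for 6-year-olds on this cream.

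**Little analysis is lost.** This largely stands. SAP 6.6 plans switcher analyses but leaves the endpoint list open, so no specified CDI-2 analysis fails. Nor does the naming of study 315 in the SAP 5.5 CDI-2 rule show that switchers were meant to have it: the DLQI rule for ages 17 and over names 315 too, which looks like repeated standard wording.

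**Conclusion.** The point holds as a cheap patient-safety improvement. Protocol footnote h, Protocol 5.1.1 and SAP 5.5 agree, so the gap at age 6 is clear on the text: permanent 0.15% dosing with no scheduled psychiatric scale.

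Under the assumptions above, about 69% of children aged 5 at Day 1 are affected. Each has on average 29 weeks on 0.15% and 2.1 clinic visits after the switch visit, 1.1 of them before exit. A figure of 3.1 visits (112/36) would include the switch visit itself, before any 0.15% is used. The absolute number cannot be derived, because no document gives the number or ages of the 315 roll-overs.

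The gain is individual screening only. There is no control arm, late starters would have no pre-roflumilast baseline, and the primary endpoints do not change.

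The age-12 point is secondary: an ambiguity with a probable C-SSRS gap. A reader might infer that these subjects lose depression monitoring. They do not: the dose is unchanged, and the CDI-2 with its thresholds and the all-age suicidality referral continue.

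**What to change.** **Main change.** Exempt the CDI-2 from the freeze in footnote h and Protocol 5.1.1 for children who switch to 0.15%. Give it at the switch visit, before the new tube is used, and at each later clinic visit, and apply the Protocol 5.1.9 thresholds. State in Protocol 5.9 that the behaviour rule and caregiver advice for ages 2 to 5 apply until the CDI-2 starts. Align SAP 5.5. Summarise late starters by observed values and the SAP 13.6 threshold proportion only, outside the change-from-baseline tables.

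**Secondary change.** State the age anchor for the C-SSRS in footnote h, Protocol 5.1.10 and SAP 13.7. Attained age is preferable: subjects who turn 12 would start it at the next clinic visit and keep the CDI-2. Only the since-last-visit version is used, so say that its first use covers the time since the previous clinic visit.

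Leave the dosing rule, laboratory tests, efficacy measures and quality-of-life scales unchanged.

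**Cost.** An IRB-approved amendment (Protocol 7.6), SAP wording, and consent or assent text if the IRB asks. The extra forms fall at existing visits, in the numbers worked out above. Any site with only 315 roll-overs would need CDI-2 forms, and any site with no subjects aged 12 or older would need C-SSRS training. Late starters would have no change score from a pre-roflumilast baseline.
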